#### Translation:

Translation of the CI-score will be managed by the lead institution with few exceptions (Turkey, Russia, Israel) and will follow the translation procedure recommended by the World Health Organization. All translations are produced by a forward–backward procedure. The latter procedure is performed to ensure, that the original meaning of the concepts is derived. The original Danish version of the CI-score has already undergone a professional translation to English. A professional translation agency will perform the translation of the English version to languages in the included countries. All questionnaires/Case Report Forms (CRF) to be filled in by patients will undergo the same translation procedure as above.

The EORTC questionnaires are available in all languages relevant to this study.

#### Data management:

A master version of the questionnaires will be collected into a booklet. On this basis, a RedCap database will be constructed to allow for direct electronic data entry by patients. Patient not able to access the web-based system, will fill in a paper version of the booklet. According to variation between populations in respect to practically illiterate's investigator lead data collection will be allowed. However, this should be agreed by the local investigation and the steering group in the planning of the data collection and included as individual amendment to the final protocol.

#### Data analysis:

Construct validity: Convergent validity will be studied by testing the CI-score on APE/Hartmann-patients against two measures of HRQoL; the anchor-questions assessing the overall stoma-impact on HRQoL, the EORTC QLQ C30 questionnaire version 3.0 and the EORTC QLQ CR29. Construct validity will furthermore be assessed by hypothesis-testing assessing the direction and magnitude of the expected correlations. Test-retest reliability will be studied on a subgroup in all included

countries. Also, we will include questions on background demographics, socioeconomic status, everyday stoma care and -costs thereby enabling investigation of the practical and economic aspect of living with a stoma varying from country to country.

#### Statistical analysis:

Statistical analysis will be performed separately for each country.

The correlations between total CI-score, anchor questions and the EORTC questionnaire results will be calculated for all participating patients according to the guidelines for the scores. For each CI-score group (minor CI/major CI) the mean EORTC QLQ C30-score will be calculated, testing the overall difference of impact on HRQoL between the CI-score groups.

Using the anchor-questions, the patients are divided into two HRQoL groups of those reporting no/minor or some/major impact on HRQoL. Relationship between CI-score and HRQoL group will be illustrated in box-plot for each country, where we expect statistically significant differences in median CI-score between the two HRQoL groups. Differences will be tested by Mann-Whitney U test. A contingency 2 by 2 table will be used to assess the degree of agreement between the two CI-score groups and the two HRQoL groups. Based on this, the sensitivity for the score will be calculated for each country. The added questions about irrigation and stoma-bag change frequency will be compared country-wise. Univariate regression analysis, descriptive analysis and estimation of impact on HRQoL will be performed. Test-retest reliability will be evaluated using Intraclass Correlation Coefficient and Cohens' Kappa.

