#### **Material and methods:**

International validation will be conducted as a retrospective cohort study. Local health care professionals will identify includable patients and register relevant clinical information on each patient from the hospital chart. Most centres will include patients from national or regional databases, some will however include conveniently if a database is not available. Our international collaborators will be responsible for sending out and collecting the questionnaires and returning the completed questionnaires to the undersigned. In countries with sufficient internet accessibility and -infrastructure the data collection will be web based i.e. patients are sent a link to the redcap-database for them to enter their answers directly. Some centres will employ paper versions of the questionnaires. In areas with substantial number of illiterates investigator led interviews can be performed.

**Inclusion criteria:** Patients who were operated with curative intent for rectal cancer with APE, Hartmann's procedure or pelvic exenteration will be included retrospectively aiming at 250 patients from each of the participating countries. This number is based on a calculation of strength based on the results from the development of the CI-score. (mean EORTC score in the major CI-group: 72. SD: 22. Minimal clinical difference: 10 points. Alpha: 0,05 STATA => sample size 206 patients. Expected dropout: 20%). Accessibility to cohorts of interest may differ between countries. Therefore, number of patients and mode of contact to patients should be agreed by the local investigation and the steering group in the planning of the data collection and included as individual amendment to the final protocol. In Denmark patients operated from January 1st 2001 to December 31st 2016 will be included.

**Exclusion criteria:** Age less than 18 years, known disseminated or recurrent disease, mental dementia and the inability to understand the actual language.

As the CI-score is a construct based on a formative model, statistical analysis based on the Classical

Test Theory (CCT) and Item Response Theory (IRT) cannot be applied. However, the following aspects of validity and reliability from the COSMIN checklist can and will be evaluated:

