*Content validity:* Comprehensiveness and relevance of the questions in the CI-score have been ensured with the way of the development of the CI-score with the starting point in a Basic Stoma Questionnaire developed by an expert group supplemented by patients ensuring that all possible factors affecting stoma function/impact was included before regression analysis lead to the seven weighed questions. After translation and cross-cultural adaptation face-validity of each translated CI-score will be assessed again by the collaborators before inclusion of patients.

*Construct validity:* This will be tested with hypothesis-testing. The following a priori formulated hypotheses on the construct validity will be tested:

- With a cut-off at 10 point the CI-score will have a sensitivity of at least 85% and a specificity of at least 50% of identifying patients with substantial colostomy impact as measured by the anchor questions (Anchor 1: poor/very poor satisfaction, remaining: Some/major impact).
- Patients with a CI-score of  $\geq 10$  have significant higher scores than patients with CI-score of  $< 10$  on all scales on the EORTC-QLQ-C30 questionnaire and this difference is clinically relevant in global health status, role functioning, social functioning and fatigue.
- Patients with a CI-score of  $\geq 10$  have significant higher scores than patients with CI-score of  $< 10$  on all scales on the EORTC-QLQ-CR29 and this difference is clinically relevant in stoma care problems.
- Patients with a CI-score of  $\geq 10$  have significant worse index value in the EQ-5D-L compared to patients with a CI-score of  $< 10$ . The sensitivity and specificity are expected to be comparable to when comparing to the anchor questions (hypothesis #1).
- The sensitivity and specificity are expected to be the same across all countries performing the validation.
- Men and women have the same relation between CI-score and HRQoL.
- If stoma care products confer a financial burden on the household the CI-score will show poorer correlation with HRQoL compared to patients where stoma care products do not confer a financial burden on the household.
- If the patients' religious affiliation or practice conflicts with having a colostomy, the CI-score will have a poorer correlation to HRQoL compared to patients who are not religious or if their religious practice does not conflict with having a stoma.

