- Patients who had their colostomy in the acute setting will have a poorer correlation between CI-score and HRQoL compared to patients operated in an elective setting.
- Patients who postoperatively had serious complication to their surgery (Clavien-Dindo  $\geq$  IIIb) will have a poorer correlation between CI-score and HRQoL compared to patients with no or minor complications.
- The following hypotheses on differences in HRQoL between different groups will be tested:
- Women colostomates have inferior HRQoL than men
- Obese patients ( $BMI \geq 30 \text{ kg/m}^2$ ) have inferior HRQoL than patients with a  $BMI < 30 \text{ kg/m}^2$
- Patients who perform their everyday stoma care themselves have a better HRQoL than patients who require help.
- Patients using irrigation for their stoma care have a better HRQoL than patients who do not irrigate.
- Patients who report the costs for stoma care products confer a burden on their household finances have an inferior HRQoL than patients who do not report this.

- Patients who report having the possibility to see a stoma care nurse if necessary have better HRQoL compared to patients who report not having this possibility.
- Patients who have had surgery in relation to their stoma for any reason have inferior HRQoL than patients who have not have surgery to their colostomy.
- Patients who report having a bulge in relation to their colostomy have inferior HRQoL than patients who do not report having a bulge.
- Patients who believe they have a hernia in relation to their colostomy have inferior HRQoL than patients who do not report having a hernia.

For convergent validation the CI-score will be tested against 5 anchor questions (not validated) and the EORTC QLQ C30+CR29 (validated). Cross-cultural validity: See translation section.

*Reliability:* For a randomly selected subgroup in each country the CI-score and anchor question will be administered twice with an interval of approximately 2 weeks. The two administrations will be independent and both the setting when answering and the forms of administration will be similar for the individual patient. For ensuring stable patients an extra question on recent changes in stoma function will be added to the retest.

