#### Organisation:

This project will outgo from the Research Unit, Department of Surgery, Aarhus University Hospital. Within recent years we have achieved profound experience with patient reported outcome measures (PROMs). Recently, a multidisciplinary clinic for cancer survivorship and late sequelae to cancer treatment has been established in relation to the Pelvic Floor Unit, Aarhus University Hospital. We have established cooperation with colleagues in the countries mentioned and we have written consent that they will assist us in retrieving data on retrospective cohorts in their respective countries as described above. To support the data collection and project logistics, each collaborating site (excluding Australia, Brazil, China, Egypt, Israel and Turkey) will receive a site visit

form the lead centre in the initial project phase.

Primary publications on validation of the CI-score will outgo from the Research Unit, Dept. of surgery, Aarhus University Hospital in accordance with the following authors' agreement:

The international validation of the CI-score is a collaboration of researchers from 15 countries worldwide and to carry out the project more than one collaborator is needed in most countries. This compiles to a comprehensive list of names. Therefore, the output from the primary validation study as stated in this protocol will be published under the authorship of [name], [name], [name], [name], [name], [name] and the "International Collaborative Group for the Colostomy Impact Score Validation". All collaborators will be registered as authors and be PubMed searchable and citable.

It is expected that the collected data will produce ideas and new research questions might emerge from the data itself. The local collaborators are encouraged formulate new research questions and protocols regarding their national cohorts. In agreement with the steering group, such research can be published with a local investigator as first author and member(s) of the steering group as co-authors in accordance with individual agreements.

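### No pooled analysis is specified for the 14 patient-level hypotheses, and country-by-country testing is weak for the five correlation contrasts and for any uneven subgroup

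*Combined protocol and SAP*

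**What the plan says.** The bullets under Construct validity (Material and methods) are counted here in order. Numbers 1-5 concern accuracy, known-groups differences and equality across countries. Numbers 6-10 compare the relation between CI-score and HRQoL in two kinds of patient, defined by sex, financial burden, religious conflict, acute surgery or serious complication. Two examples are "Men and women have the same relation between CI-score and HRQoL" and "Patients who had their colostomy in the acute setting will have a poorer correlation between CI-score and HRQoL". Nine comparisons of HRQoL level follow, such as "Patients using irrigation for their stoma care have a better HRQoL than patients who do not irrigate". None of these 14 refers to country.

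The Statistical analysis section begins "Statistical analysis will be performed separately for each country". It names no pooled, stratified, mixed-model or meta-analytic analysis. It also says "The correlations between total CI-score, anchor questions and the EORTC questionnaire results will be calculated for all participating patients", and it mentions univariate regression without saying at what level.

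The recruitment target is "aiming at 250 patients from each of the participating countries", but this is flexible: "Therefore, number of patients and mode of contact to patients should be agreed by the local investigation and the steering group". No minimum is given. The Organisation section says that the study "is a collaboration of researchers from 15 countries worldwide". The single sample-size calculation concerns a 10-point EORTC difference. It states no subgroup shares and sizes none of the 14 hypotheses.

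**The concern.** The first aim in the Background is to identify demographic and socioeconomic factors that influence stoma impact and HRQoL. That is a question about patients across the study. If each of the 14 hypotheses is tested only within countries, the plan yields 14 x 15 = 210 tests, no study-wide estimate and no rule for combining the results.

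Two things are at stake. First, a real effect may be missed in a country because the smaller subgroup is small, or because a difference between two correlations needs more patients than one country supplies. Second, hypothesis 6 predicts sameness between men and women and has no equivalence margin. A non-significant result in a small sample could then be taken as support when it shows little either way.

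**Working it through.** **Inputs.** From Material and methods: SD 22, difference 10 points, alpha 0.05, 206 patients, 20% dropout, target 250 per country. From Organisation: 15 countries. Assumed: two-sided testing, SD 22 in every subgroup, the subgroup shares, and the correlations.

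**The plan's own figure.** Power and allocation are not stated. With two equal groups and 90% power, n per group = 2 x (1.960 + 1.282)² x 22² / 10² = 101.7. The t-test version gives 103, so 2 x 103 = 206, which reproduces the figure. Then 206 x 1.2 = 247, close to 250, and 250 x 0.8 = 200 evaluable. The calculation therefore fits an even split.

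**Mean difference of 10 points, one country of 200.** Noncentral t, with noncentrality 10 / (22 x √(1/n1 + 1/n2)):

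| Smaller group | n1 / n2 | Noncentrality | Power |
|---|---|---|---|
| 5% | 10 / 190 | 1.40 | 29% |
| 10% | 20 / 180 | 1.93 | 48% |
| 20% | 40 / 160 | 2.57 | 73% |
| 26% | 52 / 148 | 2.82 | 80% |
| 50% | 100 / 100 | 3.21 | 89% |

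**Correlation 0.6 against 0.4, one country of 200.** On the Fisher z scale the difference is 0.693 - 0.424 = 0.269, with SE = √(1/(n1 - 3) + 1/(n2 - 3)):

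| Smaller group | SE | Difference / SE | Power |
|---|---|---|---|
| 5% | 0.385 | 0.70 | 11% |
| 10% | 0.254 | 1.06 | 19% |
| 20% | 0.183 | 1.47 | 31% |
| 50% | 0.144 | 1.88 | 47% |

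At an even split, 0.5 against 0.3 gives 39% and 0.6 against 0.3 gives 76%.

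**Hypothesis 6.** With a 60:40 sex split (80 and 120 patients), SE = √(1/77 + 1/117) = 0.147. The 95% interval for the difference is then ±0.29 on the z scale, wider than the 0.27 that separates 0.6 from 0.4. Power is 45%, so a real difference of that size is missed 55% of the time.

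**Stratified over 15 countries of 200 (3000 patients), same share in each, common effect.** Combining the 15 country contrasts multiplies difference / SE by √15 = 3.87.

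- Mean difference at a 5% share: SE = 7.14 / 3.87 = 1.84 and 10 / 1.84 = 5.4, so power is above 99%. With a between-country SD of 5 points in the effect, SE = √((7.14² + 5²) / 15) = 2.25 and power is still about 99%.
- Correlation contrast: the ratios become 2.71, 4.11 and 5.71 at 5%, 10% and 20%, giving about 77%, 98% and above 99%.
- Correlation contrast with a between-country SD of 0.2 on the z scale, 5% share: SE = √((0.385² + 0.2²) / 15) = 0.112 and power falls to about 67%.
- Correlation contrast with the smaller group present in only three countries: multiply by √3 = 1.73. The ratios are 1.84 at a 10% share and 2.55 at 20%, giving about 45% and 72%.

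**The case against.** Country-wise analysis has a sound rationale. Each translated version needs its own validation, hypothesis 5 is about countries, and the Background expects stoma experience and perceived HRQoL to differ between cultures. That stands, and it is a reason to keep the country results. Reducing them to description would be partly a matter of preference.

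Four stronger readings are tempting, and the documents do not support them.

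- **Most of the 14 tests are uninformative.** No subgroup shares are given. Any of the nine mean comparisons with a smaller group of about 26% or more has at least 80% power for 10 points in a country of 200. Sex could be one. Only the five correlation contrasts are weak at every split, and only for a difference of about the size assumed.
- **The plan rules out pooling.** The opening rule favours that reading. However, the sentence about correlations covers all participants, and the regression sentence, unlike those on box-plots and sensitivity, is not tied to each country. Pooling is unspecified, not excluded.
- **Fifteen times the data are available.** The data are planned, numbers may differ by country, and 3000 is what the targets would leave after dropout. Nor do the documents say that cost burden, irrigation, nurse access or religious conflict will leave one side nearly empty in some countries. They say that care and costs vary and will be studied. If such concentration did occur, pooling would gain less.
- **Non-significance in a country will count as refutation.** The plan states no such decision rule for these hypotheses.

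**Conclusion.** The point holds as a gap in specification with a measurable cost. The plan states a by-country rule and no pooled analysis for 14 patient-level hypotheses that serve a study-wide aim. With 200 evaluable patients, the five correlation hypotheses have at most 47% power in one country for 0.6 against 0.4, whatever the split. A non-significant result on hypothesis 6 would therefore not support sameness. Of the nine mean comparisons, some may be adequately powered per country and others not, with the line near a 26% share. Stratified pooling raises power substantially if countries reach target with similar shares, and less so if a factor is concentrated in few countries or its effect varies between them. All of this rests on assumed shares and correlations and on SD 22 in every subgroup.

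**What to change.** Keep the by-country analyses, including those for hypotheses 1-5. For hypotheses 6-10 and the nine group comparisons, add to the Statistical analysis section:

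- A prespecified pooled individual-patient analysis stratified by country: country intercepts, with the factor effect (or the factor by CI-score effect for hypotheses 6-10) allowed to vary by country.
- Reporting of the pooled effect with its 95% confidence interval and the between-country SD, with the study-wide conclusion based on these.
- For hypothesis 6, a judgement from the confidence interval for the difference between men and women, not from non-significance.
- A minimum cell size for by-country tests. As a guide, at 80% power a country of 200 detects 14.5 points with 20 patients in the smaller group and 20 points with 10.
- A clear statement of whether the correlations for all participants are pooled or by country.

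The cost is SAP wording and some analysis time, with no new data. The downside is that an average effect has to be read alongside the between-country spread.

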Recently, we have developed 'The Colostomy Impact Score' (CI-score), which is a simple scoring system evaluating stoma-problems in patients with a permanent colostomy after rectal cancer surgery. It was based on direct patient-reported individual outcome measures concerned with various aspects of daily life with stoma, as mapped against overall HRQoL. 610 patients treated between 2001-2007, answered a 22-items basic stoma questionnaire and one anchor question addressing the overall stoma impact on HRQoL. Regression analyses identified 7 items/questions with significant impact on HRQoL, and each item/question was allocated a weighed scoring-value. The score comprises 7 items and has a sensitivity of 85,7% for detecting patients with significant impact on HRQoL.

This CI-score is currently available in Danish and English and was developed on a Danish population. We believe it to be a quick and reliable tool to screen patients for stoma-related negative impact on HRQoL. There is no doubt that there are significant cultural, social, religious, and demographic factors that can influence a patient's experience of life with a stoma. In addition to this, perception of an individual's HRQoL is known to differ between various populations [13], [14]. Therefore, before widespread uptake of the CI-score can be promulgated, studies on reliability and validity must be performed internationally across multiple patient populations.

This retrospective cohort study has three main aims: 1) To identify demographic and socioeconomic factors influencing stoma impact and HRQoL, 2) To assess reliability and to validate the translated and cross-cultural adapted CI score internationally in multiple different centres, across a variety of patient groups and across cultural, religious, socioeconomic and physical borders and 3) To investigate if differences in everyday stoma care and -costs across countries and cultures affect CI or HRQoL.

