### **International validation of the Colostomy Impact Score**

**Objectives:** To study the influence of diversity in demographic, religious and socioeconomic factors as well as everyday stoma care on CI-score and HRQoL between countries and cultures.

Furthermore, to study the reliability and validity of the CI-score in different countries (Australia, Brazil, China, Denmark, Egypt, Israel, The Netherlands, Lithuania, Portugal, Russia, South Africa, Spain, Sweden, Turkey and the UK) by testing the CI-score against validated measures of quality of life and including test-retest reliability.

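### Aim 1 and the Objectives ask which factors influence CI-score and HRQoL, but the only regression named is univariate and no adjustment is planned

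*Combined protocol and SAP*

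**What the plan says.** The Background section says "This retrospective cohort study has three main aims". Aim 1 is "To identify demographic and socioeconomic factors influencing stoma impact and HRQoL". Aim 2 is reliability and validation of the score. Aim 3 is "To investigate if differences in everyday stoma care and -costs across countries and cultures affect CI or HRQoL". The Objectives paragraph opens with the same kind of question, "To study the influence of diversity in demographic, religious and socioeconomic factors as well as everyday stoma care on CI-score and HRQoL", and only then turns to validation.

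On design, Material and methods states: "International validation will be conducted as a retrospective cohort study". None of the factors of interest is allocated at random.

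The Statistical analysis section sets a separate analysis for each country. It names correlations, a Mann-Whitney U test, a 2 by 2 table with sensitivity, a country-wise comparison of irrigation and bag-change frequency, ICC and kappa. Its only sentence on regression is "Univariate regression analysis, descriptive analysis and estimation of impact on HRQoL will be performed". It names no factor, outcome or covariate.

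The hypotheses under Construct validity include nine HRQoL group contrasts: sex, obesity, self-care, irrigation, cost burden, access to a stoma nurse, stoma surgery, bulge and hernia.

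**The concern.** A question about what influences an outcome is not answered by a crude group difference when the groups also differ in other ways that matter for the outcome. Socioeconomic status goes with age. Cost burden goes with socioeconomic status. Irrigation and needing help with stoma care plausibly go with age, body build, acute surgery and complications. For such factors the univariate estimate mixes the factor with everything else that differs, and recruiting more patients does not remove the mixture.

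At stake are the conclusions on aim 1 and any within-country statement about stoma care or cost. For example, patients burdened by stoma costs may report lower HRQoL because of their general socioeconomic position, and the report could blame the cost of the products.

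**Working it through.** **1. Question against method.** Aim 1 and the Objectives use the language of influence. The Statistical analysis section names univariate regression. I looked for multivariable regression, covariate adjustment, matching or stratification for confounding anywhere in the document and found none. The regressions mentioned in the Background and under Content validity belong to the original development of the score.

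**2. Reach of the regression sentence.** It follows directly after the irrigation and bag-change questions and may cover only those. On that reading aim 1 has no named regression at all. On either reading, no adjustment is planned.

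**3. The plan's own figure.** Material and methods gives "mean EORTC score in the major CI-group: 72. SD: 22. Minimal clinical difference: 10 points", alpha 0.05 and 206 patients. A two-sided two-sample t-test with 103 per group has 90% power for 10 points at SD 22, and 2 × 103 = 206, so the figure reproduces. Power and sidedness are not stated and are inferred from this match.

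**4. Illustration of the bias.** The SD of 22 and the 10-point minimal clinical difference come from the plan. The SD is quoted beside the major-CI mean, so using it for other groupings is an extrapolation. Everything about the confounder is assumed.

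- Bias = confounder effect × difference in prevalence = 10 × (0.60 − 0.20) = 4 points. For a 5- or 15-point confounder it is 2 or 6 points.
- Standard error of the crude difference = 22 × √(1/n1 + 1/n0).
- The last three columns give the chance of a significant result at two-sided 5% when the factor has no effect (noncentral t).

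| Group sizes | SE | 95% half-width | Bias 2 | Bias 4 | Bias 6 |
|---|---|---|---|---|---|
| 10 vs 90 | 7.33 | 14.4 | 5.8% | 8.4% | 12.8% |
| 20 vs 180 | 5.19 | 10.2 | 6.7% | 12.0% | 21.0% |
| 103 vs 103 | 3.07 | 6.0 | 10.0% | 25.5% | 49.5% |

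Four points is below the 10-point threshold. It would, however, make a true 6 look like 10, or like 2 if the bias ran the other way.

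**5. What adjustment would achieve.** In simulation (20,000 runs per setting, 10-point confounder, no true factor effect), adjusting for the confounder measured without error returns the rejection rate to about 5%. The standard error rises by about 3% (10 vs 90 and 20 vs 180) or 8% (103 vs 103).

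If the confounder is misrecorded, part of the bias stays: residual bias = 10 × (0.40 − λ × d). Here d is the difference in recorded prevalence, and λ is the within-group slope of the true on the recorded confounder.

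- Recorded correctly in 90%: d = 0.58 − 0.26 = 0.32. For a 10:90 split λ = 0.1344/0.1975 = 0.680, leaving 1.82 points. For a 1:1 split λ = 0.160/0.218 = 0.734, leaving 1.65.
- Recorded correctly in 80%: d = 0.56 − 0.32 = 0.24. λ = 0.457 leaves 2.90 points (10:90) and λ = 0.517 leaves 2.76 (1:1).
- Simulated rejection is then about 7% to 8% (90% correct) and 8% to 14% (80% correct) at 20 vs 180 and 103 vs 103.

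**The case against.** **Unadjusted contrasts suit this study.** The HRQoL group contrasts sit under construct validity and are worded as differences between groups. Crude known-groups comparisons are normal there, and can help find patients who need attention. This stands: the contrasts are acceptable as descriptions, sex needs little or no adjustment, and aim 2 is outside this point. What remains is the mismatch between the influence wording of aim 1 and the Objectives and an unadjusted analysis.

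**Aim 3 is not a within-country question.** A reader might infer that aim 3 suffers the same fault and would be cured by the same models. The documents do not support that. Aim 3 is worded across countries and cultures, and the Objectives end with "everyday stoma care on CI-score and HRQoL between countries and cultures". A within-country version is an inference from the irrigation, self-care and cost contrasts together with the country-wise analysis. Within-country models leave aim 3 as worded unanswered.

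**The wording is loose.** Univariate can mean a single outcome, and the phrase on estimating impact is undefined and does not exclude adjustment. That is fair: the absence of planned adjustment is certain, while the reporting of confounded estimates is only what follows if the text is applied as written.

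**The figures prove nothing about this study.** That also stands. The confounder's strength and prevalence are invented, nothing supports an even split for irrigation, cost burden or needing help, and no figure concerns CI-score. For the uneven splits the 4 points lie well inside the confidence interval.

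**Conclusion.** The point holds for aim 1 and for the demographic, socioeconomic, religious and stoma-care factors in the Objectives, wherever a factor is tied to other patient characteristics. It extends to stoma-care and cost factors only if they are interpreted as influences within a country.

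The conclusion rests on the text: influence is asked about, the design is observational, and adjustment appears nowhere. It does not rest on the illustration. The size and direction of confounding here are unknown, so the rejection rates show the mechanism and are not predictions.

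A reader might also infer that the score validation or the listed group contrasts are unsound. They are not. The title, the sample size and the primary publications centre on validation, which this leaves intact. The matter should be settled before analysis, and the remedy is modest.

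**What to change.** In the Statistical analysis section, for each factor to be interpreted as an influence:

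- Prespecify a multivariable linear regression within each country for two outcomes: EORTC QLQ-C30 global health status, a scale the hypotheses already single out, and CI-score. For CI-score, use robust standard errors or check its distribution, since the plan otherwise compares it by medians.
- Give a short covariate list per factor. Examples: socioeconomic status with age and sex; cost burden with age, sex and socioeconomic status; irrigation or needing help with age, sex, BMI, acute or elective setting and serious complication; sex unadjusted.
- Leave out consequences of the factor; in particular, do not adjust HRQoL for CI-score.
- Report the univariate estimates alongside. Where a cohort is small or a factor uncommon, shorten the list or report the factor descriptively.

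The between-country part of aim 3 needs its own pooled or between-country analysis, or should be reported as descriptive. If no adjusted model is added, state aims 1 and 3 and their conclusions as unadjusted associations; that is only a wording change and removes the mismatch.

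**Cost.** One paragraph and a covariate table. The covariates come from chart data, from variables the hypotheses already need, and from the demographic and socioeconomic questions under Data analysis. The case report form is not in the document and the measure of socioeconomic status is not described, so it cannot be confirmed that no new item is needed.

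Scripted fits number (factors interpreted as influences) × 2 outcomes × 15 countries. The eight listed contrasts other than sex would give 8 × 2 × 15 = 240. That is not an upper bound, because socioeconomic status, religion, other demographics and bag-change frequency lie outside that list.

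Expect some loss of precision (3% to 8% on the standard error for one confounder in the illustration, more with longer lists), patients lost to missing covariates, and residual confounding from unrecorded or poorly measured characteristics.
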